9.4. Stopping Guidelines

Statistical monitoring of grade III-IV CTCAE toxicity or grade 3-4 CRS toxicities related to T cells is employed. Safety guideline and the rule for halting the accrual will be implemented separately for each cohort. The guidelines serve as a trigger for consultation with the FDA for additional review, and are not formal "stopping rules" that would mandate automatic closure. Additionally, after consultation with the FDA, the PI can stop the study early.

In Group C, it is extremely unlikely that patients who receive their first T cell infusions will not undergo surgical resection since all imaging studies and a clinical plan will be determined prior to infusion and it is unlikely that the T cells will cause inflammation precluding/delaying subsequent surgical resection. The accrual to Cohort C will be halted if any patient experiences a delay in subsequent surgical resection due to toxicity related to the T-cell infusion and this issue will be discussed with the FDA to develop a plan. The plan would be submitted to the DRC and IRB prior to resuming accrual to Cohort C.

10.0 MODIFIED FOLLOW-UP AND OFF STUDY CRITERIA

10.1 Criteria for Modified Follow-Up

The following criteria will result in the patient being ineligible for further treatment on the protocol, although response data will continue to be collected as applicable.

10.1.1 Any patient who develops grade III-IV toxicity related to multiTAA T cells . In such patient the toxicities will be followed until resolution or until their off study date. Although no toxicity has been associated with the infusion of this product in patients with Hodgkin and non-Hodgkin lymphoma or multiple myeloma, we will actively look for evidence of any adverse events, such as cytokine release syndrome.

10.1.2 Any patient who receives any other hematopoietic cell product excluding blood or platelets. In such patients, adverse event data collection will cease.

- 10.1.3 Any patient who experiences Grade 3 or 4 cytokine release syndrome that persists beyond 72 hours. In such patients, the toxicity will be followed until resolution or until their off study date.
- 10.1.4 Any patient whose disease progresses (based on RECIST criteria) and who receives another therapy. In such patients, adverse event data collection will cease.
- 10.1.5 If the patient desires to discontinue treatment or if the physician feels that it is in the best interest of the patient.

Patients who meet modified follow-up criteria remain on long-term follow-up as per the Summary of Monitoring (see table in Section 7.3.1)

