7.0 PATIENT EVALUATION

7.1 Follow-up Interval

Patients shall be seen in clinic prior to each T cell infusion and evaluated (seen in clinic or contacted by research coordinator) at 1 and 2 weeks after each infusion, week 4, 6, and 8 after the last infusion and then at 3, 6, 9 and 12 months after the last infusion. Study-related blood draws will cease 12 months after the last T cell infusion but we will then continue to follow patients clinically for up to 4 additional years (total of 5 years follow-up) to evaluate long-term disease responses. If persistence of cells is noted at the 12 month visit, additional follow up will be added. Additional visits will be obtained as clinically indicated.

- 7.2 A complete history and physical examination is necessary prior to administration of multiTAA T cells. Medical history will be obtained at every follow-up visit and will be reviewed annually for 5 years.

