BUN, creatinine, bilirubin, SGOT, SGPT, alkaline phosphatase, Na, K, Cl, CO ₂ , albumin, total protein, CA 19-9 [§]	x				x			x			
Imaging [^]											
Immune Function [⊥]	x	x	x		x	x	x		x	x	x
Pregnancy test [#]											

Generic Long term follow-up Table

Study timepoint (after last infusion)	Wk4	Wk6	Wk8	Mth 3, 6, 9, 12	Yr 2, 3, 4, 5
T cells					
History	x	x	x	x	x
Physical					
CBC/diff					
BUN, creatinine, bilirubin, SGOT, SGPT, alkaline phosphatase, Na, K, Cl, CO ₂ , albumin, total protein, CA 19-9 [§]					
Imaging [^]					
Immune Function [⊥]	x	x	x	x	
Pregnancy test [#]					

SOC = Standard of care

* Following this study time point monitoring will be performed per long term follow-up Table & For Group C the 1st infusion occurs at 4 weeks prior to surgery with a provision to infuse up to 1 week earlier to allow for variations in surgery scheduling.

% For Group C the 2nd infusion will occur 8 weeks post-surgery

[^]See Section 7.3.3. Imaging studies can be performed within 8 weeks of T cell administration and post-infusion monitoring will be per standard of care

[⊥] See Section 7.3.4

[#] See Section 7.3.2

\$ Or any other serum tumor marker that is elevated because of the pancreatic tumor (such as CEA or CA-125)

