9.3.3. Analysis of expansion and persistence of the adoptively-transferred TAA-specific T cells

Summary statistics such as mean \pm SD, medians and ranges will be calculated at pre- and post-infusion time points to evaluate the T cell expansion and persistence based on the immunological parameters including phenotype and T cell frequencies by ELispot and multimer studies, functional analyses (antigen-specific cytotoxicity and cytokine release) by chromium release assays and ELispot/intracellular cytokine staining, and the levels of serum cytokines.

Changes in each of the immunological parameters from pre-infusion to each time point of post-infusion will be assessed and compared using paired t-tests, or when appropriate, the Wilcoxon signed ranks test. Paired comparisons of these T cells within a patient at each time point will also be performed. These analyses will be performed in each disease group and in the overall patient group.

Plots of growth curves will be generated to graphically illustrate patterns of T-cell expansion and persistence. Longitudinal modeling techniques such as the random coefficient mixed model will be employed to model each of the repeatedly-measured T cells. These models account for variation in individual-level intercepts and slopes over the follow-up time. Thus, we will be able to model proliferation of T cells over time and estimate the magnitude of expansion or decline of T cells. Correlations between frequencies of these immunological parameters at each time point of follow-up will be assessed using measures of correlation coefficients.

Alternative strategies to analyze these immunological parameters include calculation of area under the curve over time or piecewise longitudinal models based on apparent trends from plotsof growth curves. Despite the small patient numbers, a data-dense study will be generated due to the repeat measurements on proliferation, immune function, and other parameters on each patient. The modeling strategies proposed here are amenable to these types of data but will however be considered exploratory and interpreted with caution due to limited study power. The

validity of the normality assumption on these data will be tested and appropriate transformations will be considered whenever indicated.

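### Section 9.3.3 does not separate immune samples taken after another cell product, or after progression with another therapy, so the late expansion and persistence summaries can include effects of the later treatment

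*Combined protocol and SAP*

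**What the plan says.** Section 10.1 lists events that make a patient ineligible for further study treatment, "although response data will continue to be collected as applicable". Two matter here.

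- 10.1.2: "Any patient who receives any other hematopoietic cell product excluding blood or platelets. In such patients, adverse event data collection will cease".
- 10.1.4: "Any patient whose disease progresses (based on RECIST criteria) and who receives another therapy". Adverse event collection again stops.

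For neither event does 10.1 say that immune sampling stops. It closes with "Patients who meet modified follow-up criteria remain on long-term follow-up as per the Summary of Monitoring". The pointer it gives is to a table in 7.3.1. That section has no table; the Summary of Monitoring is 7.4.

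The long-term follow-up table in 7.4 marks immune function at weeks 4, 6 and 8 and months 3, 6, 9 and 12 after the last infusion, and not in years 2 to 5. Section 7.1 ends study blood draws at 12 months, with no earlier stop for a new treatment. Section 10.2 does not make a new therapy or cell product a reason to go off study.

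On analysis, 9.3.3 states: "Changes in each of the immunological parameters from pre-infusion to each time point of post-infusion will be assessed and compared". It adds mixed models with individual slopes over follow-up and, as an alternative, area under the curve. It mentions no cut-off, flag, covariate or sensitivity analysis for later treatment.

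**The concern.** Section 9.3.3 is meant to describe expansion and persistence of the transferred T cells. The assays in 7.3.4 (multimers, ELIspot, intracellular cytokine staining, cytotoxicity) measure specificity and function, and the documents describe no marker that tells infused cells from others. A change in frequency after another cell product or a new therapy therefore cannot be assigned to the study product from the assay alone. If such samples are pooled with the rest, a rise after another cell product could look like persistence, and a fall after a new therapy could look like loss.

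Patients who meet 10.1.4 have progressed by definition. For that trigger the mixing is tied to outcome and could distort any reading of persistence against clinical course. The 10.1.2 trigger does not require progression. What is at stake is the interpretation of the late time points for objective 2.4, and for objective 2.5 in so far as it uses the same blood.

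**Working it through.** The plan gives no figure on this point to reproduce. The check is a reading of the linked sections followed by a count of draws.

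**Step 1: the chain of text.**

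| Question | Where | Answer |
|---|---|---|
| Does the patient stay in follow-up? | 10.1, 10.2 | Yes, on the long-term table |
| Does that table draw immune samples? | 7.4 | Yes, 7 time points to month 12 |
| Does a new treatment end the draws? | 7.1, 10.1 | Not stated |
| Does the analysis separate these samples? | 9.3.3 | No |

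**Step 2: post-infusion draws for a Group A patient who completes six infusions.** From the Group A table in 7.4, the immune-function row is marked at weeks 1, 2, 4, 5, 6, 8, 9, 10, 12, 13, 14, 16, 17, 18, 20, 21 and 22, which is 17 draws. Adding the 7 long-term draws gives 17 + 7 = 24. If all long-term draws follow the new treatment, the share is 7/24 = 29%. The Group B table as extracted shows one more mark, at week 7, which may be an extraction artefact; it would give 7/25 = 28%.

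**Step 3: dependence on when the new treatment starts.** Take months 3, 6, 9 and 12 as weeks 13, 26, 39 and 52, so the long-term draws fall at weeks 4, 6, 8, 13, 26, 39 and 52 after the last infusion. The start dates below are assumed. A draw on the start date itself is counted as before the treatment.

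| New treatment starts (weeks after last infusion) | Long-term draws after it | Share of 24 |
|---|---|---|
| before the week 4 draw | 7 of 7 | 29% |
| week 4 | 6 of 7 | 25% |
| week 8 | 4 of 7 | 17% |
| week 13 | 3 of 7 | 12.5% |
| week 26 | 2 of 7 | 8% |
| week 39 | 1 of 7 | 4% |

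For a patient who stops after infusion 2 the earlier draws are weeks 1, 2, 4, 5 and 6, so the upper bound is 7/(5 + 7) = 7/12 = 58%, on the same condition of a start before the week 4 draw.

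**Step 4: what mixing could do to a group summary (assumptions only).** Suppose 15 patients are sampled at a visit, k of them after another treatment, and that treatment shifts their T-cell frequency by d on the log10 scale. The group geometric mean is then off by a factor 10^(k·d/15).

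- k = 1, d = 0.5: 10^(0.033) = 1.08-fold.
- k = 3, d = 0.5: 10^(0.100) = 1.26-fold.
- k = 5, d = 1.0: 10^(0.333) = 2.15-fold.
- k = 8, d = 1.0: 10^(0.533) = 3.41-fold.

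The documents give neither k nor d. The range shows only that the effect runs from negligible to material, depending on how many patients are involved.

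**The case against.** The strongest reply has five parts.

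1. **The plan does not say that later cells count as study cells.** This stands. A reader might infer that 9.3.3 deliberately attributes post-treatment samples to the infused product. No section says so; the mixing follows from a missing rule. A reader might also infer that adverse event collection stops because attribution is no longer possible, and that the plan is therefore inconsistent. Section 10.1 gives no reason for stopping, so that argument is not available.

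2. **Continued immune sampling is itself an inference.** Partly stands. Section 10.1 names only response data as continuing, and its table reference is wrong. But it keeps these patients on the Summary of Monitoring, and the long-term table there includes immune draws. Following the plan as written produces the samples.

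3. **Concurrent treatment is part of the design.** Stands as a limit on what any cut-off can achieve. Group A is infused in the off week of ongoing chemotherapy, and Group C shows standard of care between post-operative infusions. Objective 2.5 also looks for endogenous responses. Removing samples after a 10.1.2 or 10.1.4 event does not leave a clean measure of infused cells. A cut-off at any new anticancer therapy could even truncate Group C at planned post-operative care, if that care is chemotherapy; the documents do not say.

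4. **Truncation brings its own bias.** Stands. Late time points would come mainly from patients who have not progressed. That argues for showing both versions, not for leaving the samples unmarked.

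5. **The analyses are exploratory.** Stands as to weight. But the caution in 9.3.3 concerns limited power, which does not address confounding by a later treatment.

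**Conclusion.** The gap is real and minor. Patients who meet 10.1.2 or 10.1.4 stay on a schedule with immune draws up to month 12, and 9.3.3 pools every post-infusion time point. The late summaries can therefore include effects of the later treatment.

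The 29% (7 of 24) is an upper bound that needs the new treatment to start before the week 4 draw. Later starts leave 4, 3, 2 or 1 of the seven long-term draws affected, under the assumed dates and the month-to-week conversion. The documents do not say how many patients will be affected, or how often another cell product will be given.

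Three stronger readings are not supported. Not all affected patients will have progressed, because 10.1.2 does not require it. No primary safety or feasibility result, and no progression-free or overall survival result, depends on these samples. And the rule in 7.1, "If persistence of cells is noted at the 12 month visit, additional follow up will be added", does not need the same restriction: it only adds follow-up, and no harm from its present wording is shown.

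**What to change.** Add to 9.3.3:

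- Flag every immune sample taken after the date of a 10.1.2 or 10.1.4 event. For 10.1.4, define that date as the start of the other therapy in a patient who has progressed.
- State that protocol-planned standard of care in Groups A and C does not trigger the flag.
- Report the paired tests, the mixed model and the area under the curve with and without flagged samples, and list the flagged samples separately.

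Leave the 7.1 trigger unchanged. While editing, correct the cross-reference in 10.1 from 7.3.1 to 7.4.

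The cost is a few sentences and one extra run of each analysis. Section 11.0 already calls for records of subsequent interventions, and 10.1 cannot be applied without knowing that another treatment was given; the start date should be an explicit data item. The restricted analysis will have fewer samples at late time points, mostly from patients who have not progressed, so neither version should be shown alone.

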10.2 OFF STUDY

- 10.2.1 Completion of study-specified procedures.
- 10.2.2 Refusal of study follow up by patient/Patient withdrawal of consent
- 10.2.3 Lost to follow up
- 10.2.4 Death

Any questions regarding patients on this study should be addressed to [name] at [contact].

11.0 RECORDS TO BE KEPT

The CAGT research nurse/coordinator will maintain a database documenting on study information, adverse events, off study notification and death information. The dates and doses of therapy as well as clinical chemistries, hematologic parameters, the clinical status and occurrence of any adverse events and subsequent interventions are to be kept on all patients.

- Imaging reports
- Surgical summaries
- Autopsy summaries, where appropriate
- Informed consent documents

All required clinical evaluation records will be the responsibility of Principal Investigator who will also be responsible for analysis of the clinical outcome and toxicity.

The laboratory evaluation of immunological efficacy will be the responsibility of Drs. [name] and [name].

12.0 REPORTING REQUIREMENTS

- 12.1 Register all patients with Cell and Gene Therapy Research Coordinator.
- 12.2 Enter all patients by phoning [name]. The following data will be captured:
 - Eligibility
 - Pre-study
 - Concomitant Medication
 - Adverse event

CRS Adverse Event (if applicable)
Off study
Death

12.3 Drug Toxicity and/or Adverse Reactions

- 12.3.1 Toxicity Grading: The criteria listed in the CTEP (Version 4.X) of the NCI Common Toxicity Criteria Scale will be used in grading toxicity with the exception of CRS toxicities that are related to T-cell infusions. CRS toxicities will be graded according to Appendix I.
- 12.3.2 The CTEP CTCAE (Version 4.X) is identified and located on the CTEP website at: http://ctep.cancer.gov/protocolDevelopment/electronic_applications/ctc.htm.
- 12.3.3 Adverse events will be collected as per SOP J 02.05.XX and J 02.75.XX. Data on adverse experiences/toxicities regardless of seriousness, must be collected for documentation purposes only for 8 weeks after the last dosing of study drug/biologic.
- 12.3.4 Serious adverse events will be collected as per SOP J 02.06.XX.

13.0 INFORMED CONSENT

All patients must sign a document of informed consent consistent with local institutional and Federal guidelines stating that they are aware of the investigational nature of this protocol and of the possible side effects of treatment. Further, patients must be informed that no efficacy of this therapy is guaranteed, and that unforeseen toxicities may occur. Patients have the right to withdraw from this protocol at any time. No patient will be accepted for treatment without such a document signed by his or her legal guardian. Full confidentiality of patients and patient records will be provided according to institutional guidelines

Appendix I - Grading of CRS

CRS Grading Scale

Grade	Symptoms
1	
• Symptoms are not life threatening and require symptomatic treatment only (e.g. fever, nausea, fatigue, headache, myalgia, malaise)
2	
• Symptoms require and respond to moderate intervention• Oxygen requirement <40% or hypotension responsive to fluids or low dose of one vasopressor or Grade 2 organ toxicity
3	
• Symptoms require and respond to aggressive intervention• Oxygen requirement \geq 40% or hypotension requiring high dose or multiple vasopressors or• Grade 3 organ toxicity or Grade 4 transaminitis
4	
• Life-threatening symptoms• Requirements for ventilator support or Grade 4 organ toxicity (excluding transaminitis)
5	
• Death
